##### **Secondary Endpoints:**

##### **Clinical Efficacy (In hierarchical order):**

1. Improvement in level of global disability (mRS distribution) at 90 ( $\pm$ 7) days.
2. Frequency of excellent functional outcome (mRS 0-1) at 90 ( $\pm$ 7) days.
3. NIHSS at 72 ( $\pm$ 12) h (or discharge if sooner; adjusted for the baseline in analysis)

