### **3.3 Rationale and assessment of endpoints**

**NIHSS:** We choose 30 ( $\pm 4$ ) h NIHSS (adjusted by baseline NIHSS) as our primary efficacy outcome measure as an ideal combination of good surrogate properties, feasibility, and strong biological rationale. NIHSS is a common surrogate marker for early-phase stroke trials ([Lyden, Lu et al. 2001](#), [Saver, Goyal et al. 2015](#), [Lapergue, Blanc et al. 2017](#), [Goldstein, Lennihan et al. 2018](#)) and, when analyzed appropriately using regression methods, ([Young, Weir et al. 2005](#), [Meyer, Broocks et al. 2020](#), [Mistry, Yeatts et al. 2020](#), [Mistry, Yeatts et al. 2021](#)) is strongly associated with patient-centered outcomes, including the 90d mRS global disability scale. A 72-hour NIHSS will be measured as a key secondary outcome to capture the prolonged neurological effects of TS23 in the subacute period. To minimize bias, the NIHSS will be assessed by a certified rater who will be blinded to the patients' study group assignment.

**Any ICH:** We choose ANY ICH to evaluate the safety of TS23 more robustly, as opposed to the commonly used symptomatic ICH outcome. In recent studies, ANY ICH is shown to be associated with worse 90-day global disability outcomes. ([Gay, Collie et al.](#)) In fact, we account for this safety outcome in our sample size and power calculations and are well-positioned to readily detect safety

---

issues with TS23. EXTEND trial data in the non-LVO subset (personal communication, [name]) and data pooled from other major thrombolytic trials (Lees, Bluhmki et al. 2010) informed our assumptions.

**mRS** analyzed as ordinal global disability scale and dichotomous excellent outcome (mRS 0-1): mRS is the most commonly used, patient-reported, functional disability outcome in acute stroke trials. (Lees, Bath et al. 2012, Lees, Khatri et al. 2016) To increase outcome comparability and minimize bias, the modified Rankin Scale assessments of global disability will be obtained at all sites using the formal, algorithmic Rankin Focused Assessment-Ambulatory (RFA-A) method by trained raters. (Saver, Filip et al. 2010)

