## **10.8 Analysis of the Secondary Endpoints**

Secondary analyses will compare all doses to control by graphing the raw and model-fitted means and 95% CI. Group means (adjusted for baseline NIHSS and age) will be plotted with 95% confidence intervals around the mean for each dose and control. No formal hypothesis testing will be performed and no p-values reported for secondary efficacy outcomes.

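### Section 10.8 describes the secondary endpoints by arm means, which conflicts with the ordinal mRS analysis in Section 3.3 and specifies no interval for dose versus placebo

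*Protocol*

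**What the plan says.** Section 3.2 lists the secondary clinical efficacy endpoints under the label "Clinical Efficacy (In hierarchical order". The first is "Improvement in level of global disability (mRS distribution) at 90" days and the second is "Frequency of excellent functional outcome (mRS 0-1) at 90" days. Section 3.3 says the mRS is "analyzed as ordinal global disability scale and dichotomous excellent outcome (mRS 0-1").

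Section 10.8 gives the analysis: "Secondary analyses will compare all doses to control by graphing the raw and model-fitted means and 95% CI". It continues: "Group means (adjusted for baseline NIHSS and age) will be plotted with 95% confidence intervals around the mean for each dose and control". It closes with "No formal hypothesis testing will be performed and no p-values reported for secondary efficacy outcomes". It names no ordinal or binary model, no effect measure against placebo, and no interval for a difference.

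Section 10.9 does specify an adjusted mean difference from control with a 95% interval for each active arm, but only for 30-hour NIHSS by subgroup. Elsewhere the protocol points to the SAP explicitly: Section 10.2.1 for the details of the primary dose-response models and Section 7.3 for missing data. Section 10.8 contains no such pointer.

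**The concern.** There are two linked problems.

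- **Ordinal mRS.** The endpoint is a distribution, and Section 3.3 promises an ordinal analysis. The only summary in Section 10.8 is a group mean, and different distributions can share a mean. A SAP that follows Section 10.8 literally would depart from Section 3.3, and the reverse also holds.
- **Comparison with placebo.** The stated comparison is a graph of one interval per arm. The reader is left to compare two intervals by eye, and this is not the same as an interval for the difference.

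At stake is the usefulness of the secondary results. Sections 2.5.3 and 10.3 look ahead to a later-phase trial if this one succeeds. The effect of each dose on 90-day disability relative to placebo, with its uncertainty, would be a natural input to planning that trial, and the stated method does not report it.

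**Working it through.** No figure in the protocol is in dispute. The check is a comparison of text plus an illustration of size.

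**1. The text**

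| Endpoint | Section 3.3 | Section 10.8 | Gap |
|---|---|---|---|
| 90-day mRS distribution | ordinal | group mean with its own interval | summary does not match the endpoint; no effect measure |
| mRS 0-1 at 90 days | dichotomous | group mean, which for a 0/1 variable is the proportion | no contrast with placebo |
| 72-hour NIHSS, continuous biomarkers | no conflict | group mean with its own interval | no contrast with placebo |

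**2. A mean does not fix the mRS distribution**

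Two constructed distributions over seven categories scored 0 to 6 (an assumption, because the protocol states no scoring):

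- A: 10, 15, 15, 20, 20, 8, 12%. Mean = 0.15 + 0.30 + 0.60 + 0.80 + 0.40 + 0.72 = 2.97. Share with mRS 0-1 = 25%.
- B: 16, 16, 9, 14, 21, 8, 16%. Mean = 0.16 + 0.18 + 0.42 + 0.84 + 0.40 + 0.96 = 2.96. Share with mRS 0-1 = 32%.

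The means are almost equal, yet B has more patients at both ends of the scale.

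**3. Arm intervals against an interval for the difference**

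Inputs:

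- Section 4.1: 300 patients, 10 per group in the burn-in, then 13 controls in each block of 50. Five blocks follow the burn-in, so control n = 10 + 5 × 13 = 75 and active n = 300 − 75 = 225.
- Assumption: an even split over four doses, 225/4, or about 56 each. The adaptive allocation will give other sizes, so a range is shown.
- Table 3: SD 5.5. This is for early NIHSS and is used only as an illustration.
- Section 10.3: a 2-point NIHSS difference is called clinically meaningful.

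Formulas: arm half-width = 1.96 × SD/√n. The arm intervals separate when the difference exceeds the sum of the two half-widths. Half-width for the difference = 1.96 × SD × √(1/75 + 1/n).

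For n = 56:

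- control: 1.96 × 5.5/√75 = 1.24
- dose: 1.96 × 5.5/√56 = 1.44
- separation needed: 2.69 from unrounded values
- difference: 1.96 × 5.5 × √(1/75 + 1/56) = 1.90

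| Dose n | Arm intervals separate at | Half-width of difference |
|---|---|---|
| 30 | 3.21 | 2.33 |
| 56 | 2.69 | 1.90 |
| 100 | 2.32 | 1.65 |
| 150 | 2.12 | 1.52 |

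At an observed difference of 2 points the arm intervals overlap in every row. The interval for the difference excludes zero at n = 56 (2.0 ± 1.90, or 0.1 to 3.9), 100 and 150. At n = 30 it does not.

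The general result agrees: two equal-width 95% intervals that just touch correspond to z = 2 × 1.96/√2 = 2.77, or a two-sided p of about 0.006.

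**4. What a contrast for mRS 0-1 would show**

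Assume 30% on placebo (n = 75) and 45% on a dose (n = 56). The standard error is √(0.30 × 0.70/75 + 0.45 × 0.55/56) = 0.085. The risk difference is 0.15 with a 95% interval of −0.02 to 0.32. With placebo rates of 20% and 40% and the same gain, the intervals are −0.00 to 0.30 and −0.02 to 0.32. These rates are assumptions, not protocol figures.

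**The case against.** The strongest reply is that Section 10.8 is a short, generic description of a display. Its heading also covers incidences such as symptomatic ICH and death, and nobody would read it as fixing a Gaussian model for those. It says model-fitted without naming a model, so an ordinal or logistic model is not excluded. It says doses are compared with control, and any model that yields adjusted arm means also yields their contrasts. Link functions and effect measures are ordinary SAP content, and the SAP is not shown.

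Part of this stands. The protocol does not forbid contrasts or an ordinal model, and the absence of modelling detail would not by itself be a finding. What remains is that Section 10.8 positively names a summary, the group mean, and an interval, the one around each arm's own mean, without deferring to the SAP. That summary does not fit the endpoint as Sections 3.2 and 3.3 define it.

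A reader might infer more than the document supports:

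- **That mRS 0-1 is not analysed at all.** The mean of a 0/1 variable is the frequency, which is the endpoint as worded.
- **That death is averaged in as a score of 6.** The protocol states no mRS code for death.
- **That the hierarchical ordering is a broken testing procedure.** With no tests planned, the phrase can only rank importance. This is an editorial matter.
- **That leaving out p-values is a fault.** It is a legitimate choice in an early-phase trial.
- **That overlap of intervals drives a decision.** No section uses overlap as a criterion.

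**Conclusion.** The point holds in a limited form. For the 90-day mRS distribution, Section 10.8 conflicts with Section 3.3. For mRS 0-1 and the continuous secondary endpoints, the gap is only the missing interval for dose versus placebo.

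In the illustration, a reader relying on arm intervals would need a difference of 2.69 points to see separation, whereas the direct interval excludes zero from about 1.90. These figures rest on an SD borrowed from early NIHSS and on an assumed even split of active patients. The ordering of the two thresholds does not depend on either assumption, because the sum of two standard errors always exceeds the root of their summed squares.

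It would be wrong to infer that the trial's conclusion is at risk. The Go rule in Section 10.2.4 uses the utility built from ICH and early NIHSS, and mRS plays no part in it. The consequence is confined to what the secondary results can tell the planners of a later trial.

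**What to change.** Amend Section 10.8 to report, for each dose versus placebo, adjusted for baseline NIHSS and age, with 95% intervals and without p-values:

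- **90-day mRS:** a common odds ratio from an ordinal model, with the mRS distribution shown by arm.
- **mRS 0-1:** a risk difference or an odds ratio, naming which.
- **NIHSS and the continuous biomarkers:** the mean difference from placebo.

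The plots of arm means can stay as a supplement. The cost is revised wording and a little more analysis programming. No further data or patients are needed.

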## **10.9 Sub-Group Analyses**

Recruitment and retention of females and minorities will be monitored by the DSMB and will be provided in the Final Report. Although we do not anticipate differential treatment effects based on sex, race, or ethnicity, our analyses will explore clinically important differences due to sex/race/ethnicity.

A table/forest plot will be created which shows the following by Subgroup level:

---

Subgroup/ Number of Patients/Adjusted Mean (SD) NIHSS at 30 ( $\pm$ 4) hours for all treatment group/Adjusted Mean difference from control (95% CI) for each active arm.

## **10.10 Sensitivity Analysis**

As a sensitivity analysis the primary analysis will be repeated with the Per-protocol sample. If these analyses are not consistent with the primary Intention-To-Treat (ITT) analysis, then the trial findings will be interpreted with caution.

# **11 SUPPORTING DOCUMENTATION AND OPERATIONAL CONSIDERATIONS**

## **11.1 Regulatory, Ethical, and Study Oversight Considerations**

### **11.1.1 *Informed Consent Process***

#### **11.1.1.1 *Consent/assent and Other Informational Documents Provided to participants***

Consent forms describing in detail the study intervention, study procedures, and risks are given to the participant if they are able to provide informed consent or their legally authorized representative as soon as the study team is able to contact them.

#### **11.1.1.2 *Consent Procedures and Documentation***

Informed consent is a process that is initiated prior to the individual's agreeing to participate in the study and continues throughout the individual's study participation. SISTER trial will primarily utilize electronic consent forms. Paper consent forms will be available per site request. Consent forms will be IRB-approved and the participant or their surrogate healthcare decision maker will be asked to read and review the document. The investigator will explain the research study to the participant or their surrogate healthcare decision maker and answer any questions that may arise. A verbal explanation will be provided in terms suited to the participant's or their surrogate healthcare decision maker's comprehension of the purposes, procedures, and potential risks of the study and of their rights as research participants. Participants or their surrogate healthcare decision makers will have the opportunity to carefully review the written consent form and ask questions prior to signing. The participants or their surrogate healthcare decision makers will have the opportunity to discuss the study with their family or surrogates or think about it prior to agreeing to participate. Participants and their surrogate healthcare decision makers will be informed that participation is voluntary and that they may withdraw from the study at any time, without prejudice. A copy of the informed consent document, either physical or electronic, will be given to the participants for their records. The rights and welfare of the participants will be protected by emphasizing to them that the quality of their medical care will not be adversely affected if they decline to participate in this study.

---

### **11.1.2 Study Discontinuation and Closure**

This study may be temporarily suspended or prematurely terminated if there is sufficient reasonable cause. Written notification, documenting the reason for study suspension or termination, will be provided by the suspending or terminating party to study participants and funding agency. If the study is prematurely terminated or suspended, the PI will promptly inform study participants, the IRB, and sponsor and will provide the reason(s) for the termination or suspension. Study participants will be contacted, as applicable, and be informed of changes to study visit schedule.

Circumstances that may warrant termination or suspension include, but are not limited to:

- Determination of unexpected, significant, or unacceptable risk to participants
- Insufficient compliance to protocol requirements

Study may resume once concerns about safety, protocol compliance, and data quality are addressed and satisfy the IRB.

### **11.1.3 Confidentiality and Privacy**

Participant confidentiality and privacy is strictly held in trust by the participating investigators, their staff, and the sponsor in accordance with StrokeNet SOP GCP 05. This confidentiality is extended to cover clinical information relating to participants. Therefore, the study protocol, documentation, data, and all other information generated is held in strict confidence. No written documents related to the study (e.g., protocol, Manual of Procedures (MOP), Investigator's Brochure (IB)) or data may be released outside of the usual operations of the SISTER without the express permission of the leadership.

In accordance with subsection 301(d) of the Public Health Service Act, this research is covered by a Certificate of Confidentiality (COC), and therefore the investigators shall not disclose or provide, in any Federal, State, or local civil, criminal, administrative, legislative, or other proceeding, the name of a participant or any such information, document, or data that contains identifiable, sensitive information about a participant and that was created or compiled for purposes of the research, unless such disclosure or use is made with the consent of the individual to whom the information, document, or data pertains.

All research activities will be conducted in as private a setting as possible, within limitations sometimes imposed by the medical environment encountered as a result of acute stroke.

The medical safety monitors, DSMB, or Central Institutional Review Board (cIRB); study PIs, NCC, NDMC, or their authorized representatives; or relevant regulatory agencies may inspect all documents and records required to be maintained by the investigator, including but not limited to, medical records (office, clinic, or hospital) and supply records for the participants in this study.

---

The study participant's contact information will be securely stored at each clinical site for internal use during the study. At the end of the study, all records will continue to be kept in a secure location by performance sites and by the NDMC in accordance with the StrokeNet SOP GCP 12, or longer if required by the cIRB or local site regulations.

Study participant research data, which is for purposes of statistical analysis and scientific reporting, will be transmitted to and stored at the NDMC at the Medical University of South Carolina (MUSC). This will not include the participant's contact or identifying information. Rather, individual participants and their research data will be identified by a unique study identification number. The study data entry and study management systems used by clinical sites and by the NDMC research staff will be secured and password protected. At the end of the study, all study databases – already de-identified as above – will be archived at the NDMC (as well as archived in data repositories as described in 10.1.14). Data are collected electronically in WebDCU™, the data management system managed by the NDMC of StrokeNet.

#### ***11.1.4 Future Use of Stored Specimens and Data***

Data collected for this study is analyzed and stored at the NDMC and images collected for this study are analyzed and stored at the SISTER Imaging Core at the University of Cincinnati. After the study is completed, the archived LDS data and imaging will be transmitted to and stored in the NINDS Data Repository, for use by other researchers including those outside of the study, per StrokeNet SOP ADM 04 and in accordance with de-identification procedures of GCP 05.

Specimens will be used only for purposes related to research described in this protocol, i.e., understanding the causes and optimal prevention, treatment, and outcomes of unexplained strokes. The Executive Committee reviews will ensure that uses of subject specimens are consistent with the informed consent obtained at the time the specimen was collected.

#### 11.1.5.1 Safety Oversight

Safety oversight is under the direction of the NINDS-appointed DSMB, composed of individuals with the appropriate expertise, including expertise in stroke and biostatistics. Members of the DSMB are independent from the study conduct and free of conflict of interest, or measures should be in place to minimize perceived conflict of interest. The DSMB operates under the rules of an approved charter to be written prior to, and reviewed at, the organizational meeting of the

DSMB. The DSMB provides its input to NINDS/NIH staff, as well as the PIs of the SISTER trial. The NIH StrokeNet DSMB-IRB SOP can be found at <https://www.nihstrokenet.org/docs/default-source/default-document-library/strokenet-cirb-and-dsmb-joint-operating-procedure-9-15-2020.pdf?sfvrsn=0>.

Changes in the constitution of the DSMB will not trigger a cIRB protocol amendment. Additionally, SISTER MPIs have named an IMM, who will review safety events including SAEs on an ongoing basis.

### **11.1.6 Clinical Monitoring**

Clinical site monitoring is conducted to ensure that the rights and well-being of human participants are protected, that the reported trial data are accurate, complete, and verifiable, and that the conduct of the trial is in compliance with the currently approved protocol/amendment(s), with GCP, with applicable FDA regulations (21 CFR 312), and with the FDA's "Guidance for Industry Oversight of Clinical Investigations — A Risk-Based Approach to Monitoring."

- Monitoring for the trial will be performed by the NDMC centrally, on site, and remotely.
  - Per the study's monitoring plan, monitoring will include a combination of on-site monitoring (to verify data entered into the WebDCU™ database against source documents and query inaccuracies between the source documents and WebDCU™ database), remote monitoring (source document verification, including verification of written consent, may be performed remotely by reviewing source documents that have been uploaded into WebDCU™ or via remote access to electronic medical records), and central monitoring (using web-based data validation rules, data manager review of entered data, statistical analysis, and on-going review of site metrics).
  - The NDMC, study PIs, project managers, and the appropriate site PIs will be provided copies of monitoring reports within 30 days of site visits.
  - In an effort to review informed consent forms in a timely manner, enrolling sites will upload a pdf of the signed informed consent form, into the password protected clinical trial management system, WebDCU™. The PDF file will be linked to the subject ID but will be stored on a secure server separate from the study's CRF data. The secure server on which these files are stored is not backed up to prevent copies of files containing individually identifiable health information from being copied and stored on non-NDMC back up servers. The files on these servers can only be accessed by designated NDMC study personnel. NDMC staff will remotely monitor the informed consent forms and issues identified will be relayed to the clinical site for corrective and preventative action. After remote monitoring is complete, the PDF file containing the informed consent form will be permanently deleted from the secure server. If a subject must be re-consented, the process will repeat itself.
-

### **11.1.7 Quality Assurance (QA) and Quality Control (QC)**

Each clinical site will perform internal quality management of study conduct, data and biological specimen collection, documentation, and completion. An individualized quality management plan will be developed to describe a site's quality management.

Quality control (QC) procedures will be implemented beginning with the data entry system and data QC checks that will be run on the database will be generated. Any missing data or data anomalies will be communicated to the site(s) for clarification/resolution.

Following written SOPs, the monitors will verify that the clinical trial is conducted, and data are generated and biological specimens are collected, documented (recorded), and reported in compliance with the protocol, ICH GCP, and applicable regulatory requirements.

The investigational site will provide direct access to all trial related sites, source data/documents, and reports for the purpose of monitoring and auditing by the sponsor, and inspection by local and regulatory authorities.

### **11.1.8 Data Handling and Record Keeping**

#### **11.1.8.1 Data Collection and Management Responsibilities**

Data collection is the responsibility of the clinical trial staff at the site under the supervision of the site investigator. The investigator is responsible for ensuring the accuracy, completeness, legibility, and timeliness of the data reported.

All source documents should be completed in a neat, legible manner to ensure accurate interpretation of data. Black ink is required to ensure clarity of reproduced copies. When making changes or corrections, cross out the original entry with a single line, and initial and date the change. **DO NOT ERASE, OVERWRITE, OR USE CORRECTION FLUID OR TAPE ON THE ORIGINAL.**

Copies of the electronic CRF (eCRF) are provided for use as source documents and maintained for recording data for each participant enrolled in the study. Data reported in the eCRF derived from source documents should be consistent with the source documents or the discrepancies should be explained and captured in a progress note and maintained in the participant's official electronic study record.

Clinical data (including AEs, concomitant medications, and expected adverse reactions data) and clinical laboratory data will be entered into WebDCU™ a 21 CFR Part 11-compliant data capture system provided by the NDMC. The WebDCU™ data system includes password protection and internal quality checks, such as automatic range checks, to identify data that appear inconsistent, incomplete, or inaccurate.

---

